4.5 Expected Duration of Subject Participation in the Study

After a screening period of up to 28 days, subjects will receive a single dose of the study treatment, which will be followed by a PK sampling period of 150 days. The total duration of participation for each subject in this study will be up to approximately 178 days.

4.6 Discontinuation Criteria for Individual Subjects and Study

4.6.1 Discontinuation Criteria for Individual Subjects

See Section 5.3 Subject Withdrawal Criteria.

4.6.2 Premature Termination of Study

The sponsor, Institutional Review Board/Ethics Committee (IRB/EC), and/or regulatory authorities have the right to close this study or the study center, and an Investigator /sponsor has the right to close the study center, at any time, although this should occur only after consultation between involved parties. The IRB/EC must be informed. Should the study/center be closed prematurely, all study materials (except documentation that has to remain stored at site) must be returned to the sponsor. An Investigator will retain all other documents until notification given by the sponsor for destruction.

The study center can be closed for the following reasons:

- Lack of enrollment
- Non-compliance with the requirements of the study protocol
- Non-compliance with ICH, GCP

4.7 Accountability Procedures for Investigational Product(s)

IP is to be used only for the study in accordance with the directions given in this protocol. An Investigator, or designee such as the study pharmacist, is responsible for the distribution of the IP in accordance with directions given in the protocol.

An Investigator is responsible for maintaining accurate records of the IP for his/her site. IP inventory/dispensing documentation verifying the receipt, dispensing, damaged state or return must be maintained and kept current by an Investigator, or designee. The inventory must be made available for inspection by the monitor. IP supplies must be accounted for by the monitor and inventory/dispensing logs must be verified by the monitor prior to IP return or destruction. Written documentation of any used and unused inventory is required. At the end of the study, a copy of the inventory/dispensing log(s) will be retrieved by the monitor and returned to Grifols.

4.8 Maintenance of Treatment Randomization Codes

As this is an open-label, single-arm study design, no randomization code will be provided.

4.9 Data to Be Recorded Directly on the eCRFs

Source documents will be used to record all study-related data. Designated staff will enter the data required by the protocol into the Electronic Case Report Forms (eCRF).

5 SELECTION AND WITHDRAWAL OF SUBJECTS

This study will include HAV-seronegative healthy adult subjects.

5.1 Inclusion Criteria

A subject must meet all the following inclusion criteria to be eligible for participation in this study:

1. Male subjects from 18 to 55 years of age, inclusive, or female subjects from 18 to 65 years of age, inclusive
2. Subjects with a body mass index (BMI) of 18.5 to 29.9 kg/m²
3. Body weight greater than or equal to 50 kg at screening
4. Subjects willing and able to provide written informed consent

5. Subjects in good health in the judgment of the Investigator, as determined by medical history, physical examination, vital signs, ECG and laboratory assessments
6. A female study subject must meet one of the following criteria:
 - a. If a female of childbearing potential – agrees to use one of the accepted contraceptive regimens from at least 30 days prior to study treatment administration and during the entire study duration. An acceptable method of contraception includes one of the following:
 - Abstinence from heterosexual intercourse (i.e. when abstinence is the preferred and usual lifestyle of the subject; periodic abstinence is not acceptable)
 - Non-estrogen containing hormonal contraceptives (birth control pills, injectable/implant/insertable hormonal birth control products, transdermal patch)
 - Intrauterine device without hormones
 - Condom with spermicide
 - Diaphragm or cervical cap with spermicide
 - Vasectomized partner (minimum 6 months since vasectomy prior to study treatment administration)
 - b. If a female of non-childbearing potential – should be surgically sterile (i.e. has undergone complete hysterectomy, bilateral oophorectomy, or tubal ligation) or in a menopausal state (at least 1 year without menses prior to study treatment administration)
7. A male study subject must agree to use one of the accepted contraceptive regimens during the entire study duration;
 - Abstinence from heterosexual intercourse
 - Female partner with condom with spermicide used by male study subject
 - Female partner of non-childbearing potential
 - Male sterilization (if proof of sterilization is not provided, the subject must agree to use one of the above accepted contraceptive methods)
8. A male study subject must agree not to impregnate a female or donate sperm during the entire study duration

5.2 Exclusion Criteria

A subject meeting any of the following exclusion criteria is NOT eligible for participation in the study:

1. Subject vaccinated against HAV, as documented in medical history at the screening visit
2. Subject with positive anti-HAV antibodies in blood sample at the screening visit
3. Subject who previously received any type of IG, including HAV IG within the past 12 months prior to study treatment administration

4. Subject with prolonged International Normalized Ratio (INR) or activated partial thromboplastin time (aPTT) at the screening visit
5. Subject with a platelet count below $100 \times 10^9/L$ at the screening visit
6. Subject suffering from some acute or chronic medical, surgical or psychiatric significant condition or laboratory abnormality at the screening visit or prior to study treatment administration that, according to Investigator judgement, may increase the risk associated with study participation or study treatment administration, or may interfere with the successful completion or interpretation of the study results
7. Subject with a history of the following: angioedema, cardiac arrhythmia, angina pectoris, myocardial infarction, cerebrovascular accident, cardiac failure, thrombotic events, embolism, coagulopathy, diabetes mellitus, hyperlipidaemia, nephrotic syndrome, acute renal injury, chronic obstructive pulmonary disease, asthma, hepatic disease, reticuloendothelial system dysfunction, or nervous system disorder
8. Subject with known personal or family history of abnormal bleeding episodes
9. Subject not willing to receive study treatment via IM route of administration or unable to receive study treatment via IM route of administration
10. Subject with cardiovascular risk factors based on medical history: active tobacco smoking and/or ongoing diabetes mellitus at the screening visit
11. Subject with thrombosis risk factors: prolonged immobilization within 2 months prior to the screening visit, history of venous or arterial thrombosis, use of estrogens (30 days prior to the study drug administration), indwelling central vascular catheters and hyperviscosity or hypercoagulable states
12. Subject with known history of hypersensitivity/allergic reaction to blood/plasma products
13. Subject with known selective IgA deficiency (with or without antibodies to IgA)
14. Subject who received any plasma-derived product infusion within 12 months prior to study treatment administration
15. Subject who received a blood or plasma transfusion within 12 months prior to study treatment administration
16. Subject with systolic blood pressure >140 mmHg or diastolic blood pressure >90 mmHg at the screening visit and prior to treatment administration
17. Subject with anemia (hemoglobin <12 g/dL in women and 13 g/dL in men) at the screening visit
18. Subjects with proteinuria ($>1+$ on urine dipstick), blood urea nitrogen (BUN) or creatinine greater than the upper limit of normal at the screening visit
19. Subject with liver enzymes (aspartate aminotransferase [AST], alanine aminotransferase [ALT] and gamma-glutamyl transferase [GGT]) levels greater than the upper limit of normal at screening visit
20. Subject who received any dose of parenteral, oral, or inhaled corticosteroids, immunosuppressants, or immunomodulators within 6 weeks prior to the screening visit

21. Subject who received any live virus vaccine within five months prior to the screening visit
22. Subject not willing to postpone receiving any live virus vaccines until 6 months after receiving IP
23. Currently receiving any anti-viral treatment, regardless of the route of administration
24. Subject with virus safety laboratory results (serology and/or nucleic acid amplification technology [NAT]) indicative of a current infection with hepatitis A virus (HAV), hepatitis B virus (HBV), hepatitis C virus (HCV), human immunodeficiency virus (HIV) or parvovirus B19 (B19V) at the screening visit
25. Participated in another clinical trial within 30 days prior to the screening visit or has received any IPs within 3 months prior to the screening visit
26. Positive urine drug panel testing at the screening visit or prior to study treatment administration
27. Known or suspected abuse of alcohol, opiates, psychotropic agents or other drugs or chemical substances; or has done so in the 12 months prior to the screening visit
28. In the opinion of the Investigator, the subject may have compliance problems with the protocol and the procedures of the protocol
29. Subject who has already been included in a previous group for this clinical study

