5.3 Subject Withdrawal Criteria

5.3.1 Screen Failures

Screening evaluations will be used to determine the eligibility of each subject for enrollment. Subjects who fail to meet eligibility criteria during screening evaluations will be considered screen failures and will not participate in the study. However, subjects who fail the first screening evaluation are allowed to be re-screened once.

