7 ASSESSMENT OF EFFICACY AND PHARMACOKINETICS

7.1 Efficacy Variables

7.1.1 Primary Efficacy Variable

The primary efficacy variable in this study is the proportion of subjects maintaining protective anti-HAV antibody levels (defined as anti-HAV antibody titer ≥ 10 mIU/mL in plasma and/or serum) up to 60 days after study treatment administration.

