7.2 Pharmacokinetic Variables

The PK Variables for anti-HAV antibody in plasma and/or serum are:

- $AUC_{0-\infty}$: AUC from time zero to time infinity
- AUC_{0-T} : AUC from time zero to time of last measured concentration
- C_{max} : maximum concentration
- T_{max} : time to C_{max}
- λ_z : terminal elimination rate
- T_{half} : estimated elimination half-life
- Cl_{TOT}/F : apparent total plasma and/or serum clearance
- V_D/F : apparent volume of distribution

PK parameters will be estimated using both anti-HAV antibody baseline uncorrected and baseline corrected levels.

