7.3 Methods and Timing for Assessing, Recording, and Analyzing Efficacy Parameters

7.3.1 Observations and Measurements

The following is a description of the procedures/assessments to take place at each study visit. See the Schedule of Study Procedures and Events in [Appendix 1](#).

Screening Visit (Day -28 to Day -2):

Subjects will be screened for enrollment in this study. The following procedures will be done:

- Obtain informed consent
- Review of inclusion and exclusion criteria for determination of subject's study eligibility
- Documentation of medical history
- Documentation of demographics
- Height and weight measurement and determination of BMI
- Full physical examination (excluding breast and genitourinary examination)
- ECG

- Vital signs measurement (heart rate [HR], blood pressure [BP], respiratory rate [RR], and body temperature)
- Clinical laboratory assessments (chemistry, hematology, urinalysis) (see [Table 7-1](#) for details)
- Virus safety testing (see [Table 7-1](#) for details). Note: the viral safety test results for HAV serology (HAV antibody differential (Immunoglobulin M [IgM]/IgG)) will be used to determine subject eligibility
- Coagulation tests (INR, aPTT)
- Immunoglobulin A (IgA) testing (see [Table 7-1](#) for details)
- Urine alcohol and drug panel testing (see [Table 7-1](#) for details)
- Urine pregnancy test for females
- Record prior (30 days prior to screening visit) and concomitant medications
- Record AEs

Treatment Period:

Day -1:

Subjects will be admitted to the clinical research unit on the day prior to study drug injection. The following procedures will be done upon admission:

- Review of subject eligibility (review of inclusion/exclusion criteria)
- Record concomitant medications
- Record AEs
- Vital signs measurement (HR, BP, RR, and body temperature)
- Symptom-directed physical examination
- ECG
- Clinical laboratory assessments (chemistry, hematology, urinalysis) (see [Table 7-1](#) for details)
- Urine alcohol and drug panel testing (see [Table 7-1](#) for details)
- Urine pregnancy test for females

Day 1:

The following procedures will be done (all pre-dose procedures are to be performed within 1 hour prior to dosing):

- Collection of virus safety retain samples prior to study drug injection

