9.7 Subject Population(s) for Analysis

9.7.1 Safety Population:

The safety population consists of all subjects who received any amount of study drug.

9.7.2 Evaluable Population:

The evaluable population consists of all subjects who received the entire dose of IP and had no major protocol deviations that would impact the efficacy analysis up to Day 60. Any deviations from the protocol will be recorded in the protocol deviation list and evaluated before database lock.

9.7.3 PK population:

The PK population consists of all subjects who received the entire dose of the IP and who provided sufficient plasma and/or serum concentration data to facilitate calculation of PK parameters. Subjects who do not complete the PK sampling schedule may be included in the PK analysis only for the PK parameters that are judged not to be affected by the missing sample(s). This decision is to be documented and approved by the sponsor before the start of the sample analysis by the bioanalytical facility.

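### The quantitative Day 1 pre-dose anti-HAV titer enters neither the primary analysis nor the evaluable population, so antibody already present before dosing could be counted as protection from the product

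*Protocol*

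**What the plan says.** **Population.** Protocol 3.1 states the primary objective for HAV-seronegative healthy subjects. Exclusion 2 in 5.2 removes a "Subject with positive anti-HAV antibodies in blood sample at the screening visit". Section 7.3.1 names the test: "the viral safety test results for HAV serology (HAV antibody differential (Immunoglobulin M [IgM]/IgG)) will be used to determine subject eligibility". The visit is headed "Screening Visit (Day -28 to Day -2"), and no cut-off in mIU/mL is given. The Day -1 procedures (7.3.1, Appendix 1) repeat the eligibility review but include no HAV serology. Under 7.3.2 and 8.2.3, the virus-safety samples retained on Day 1 are tested only if symptoms of infection appear.

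**Measurement.** Table 7-2 in 7.3.3 lists 16 samples for total anti-HAV. Sample 01 is taken on Day 1 before dosing.

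**Endpoint and analysis.** Section 7.1.1 defines the primary variable as the "proportion of subjects maintaining protective anti-HAV antibody levels (defined as anti-HAV antibody titer ≥ 10 mIU/mL in plasma and/or serum") up to 60 days. Section 9.1.2 summarises that percentage in the evaluable and safety populations and mentions no baseline. For PK, by contrast, 7.2 says: "PK parameters will be estimated using both anti-HAV antibody baseline uncorrected and baseline corrected levels".

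**Analysis set.** The evaluable population in 9.7.2 is "all subjects who received the entire dose of IP and had no major protocol deviations that would impact the efficacy analysis up to Day 60". It carries no condition on the pre-dose titer.

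**The concern.** With no control arm, crediting a titer to the dose depends on the subject having had no antibody beforehand. The protocol checks this once, with a screening serology whose cut-off is not stated. The endpoint is read later as a quantitative total titer, which cannot separate a subject's own antibody from the product's.

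The more direct evidence is sample 01, measured on the endpoint's own scale just before dosing. The protocol allows for a non-zero baseline when it plans baseline-corrected PK, yet makes no use of it in the one result decided by a fixed threshold.

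The deviation filter in 9.7.2 does not close the gap. Exclusion 2 refers to the screening visit, so a subject negative then and measurable on Day 1 has broken no rule and has no deviation to classify. Own antibody can only raise the total, so any error favours the product.

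**Working it through.** **1. The plan's own figure (9.2).** 28 enrolled with about 30% dropout: 28 × (1 − 0.30) = 19.6, or about 20 evaluable. This reproduces. Section 9.2 says there was no formal calculation and 9.3 that there is no hypothesis test, so the observed percentage is the result.

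**2. Weight of one subject.** One subject is 1/20 = 5.0 points, or 1/28 = 3.6 points. If one success is recounted as a failure (exact 95% intervals):

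| n | All successes | One recounted |
|---|---|---|
| 20 | 20/20 = 100% (83.2 to 100) | 19/20 = 95% (75.1 to 99.9) |
| 28 | 28/28 = 100% (87.7 to 100) | 27/28 = 96.4% (81.7 to 99.9) |

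Removing the subject instead shrinks the denominator and moves the estimate less: 20/20 becomes 19/19, still 100%, and 18/20 = 90% becomes 17/19 = 89.5%.

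**3. Could a sub-threshold baseline matter at Day 60?** This is an illustration at minimum potency.

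- Inputs from the protocol: 0.2 mL/kg (4.4.1), minimum 20 IU/mL (4.4.1.1), half-life 23 days and peak at about 2 days (2.4.2).
- Assumptions: apparent volume V/F of 60 to 120 mL/kg, between-subject CV of 30% (lognormal), and a constant baseline of own antibody b.
- Dose: 0.2 × 20 × 1000 = 4,000 mIU/kg.
- Fraction left 59 days after dosing (Day 60): 2^(−59/23) = 0.169.
- Product-only level with immediate, complete input: 4,000 × 0.169 / V. For V/F of 60, 70, 80, 100 and 120 this gives 11.3, 9.7, 8.4, 6.8 and 5.6 mIU/mL. Own antibody needed to reach 10 is 0, 0.3, 1.6, 3.2 and 4.4.

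With first-order absorption peaking at 2 days, ke = ln 2/23 = 0.0301 and ka = 2.168 per day. The levels are multiplied by ka/(ka − ke) = 1.014, giving m = 11.42, 8.57 and 6.85 for V/F of 60, 80 and 100. With σ = √ln(1 + 0.3²) = 0.294 and m as the median, P(total ≥ 10) = Φ[ln(m/(10 − b))/σ]. For example, at V/F 80 and b = 4: ln(8.57/6)/0.294 = 1.21, so P = 0.89.

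| V/F (mL/kg) | b = 0 | b = 2 | b = 4 | b = 6 |
|---|---|---|---|---|
| 60 | 67% | 89% | 99% | 100% |
| 80 | 30% | 59% | 89% | about 100% |
| 100 | 10% | 30% | 67% | 97% |

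**4. The same model at higher potency.** 20 IU/mL is a floor. At V/F 80, moving b from 0 to 4 changes the probability as follows:

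| Assumed potency (IU/mL) | b = 0 | b = 4 |
|---|---|---|
| 20 | 30% | 89% |
| 30 | 80% | 99% |
| 40 | 97% | 100% |
| 50 | 99.5% | 100% |

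**5. How many subjects?** The protocol gives no figure. If an assumed 1%, 2% or 5% of the 28 carried such antibody, the chance of at least one is 1 − (1 − p)^28 = 24.5%, 43.2% or 76.2%.

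**The case against.** Several safeguards already apply. Section 5.2 excludes documented HAV vaccination (1), immune globulin within 12 months (3; 365/23 is about 16 half-lives), plasma products and transfusions within 12 months (14, 15) and current HAV infection by serology or NAT (24). Undocumented vaccination must still pass the screening serology. What remains is antibody that appears within at most 28 days, or antibody below the unstated screening cut-off. That stands: affected subjects should be few or none.

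A pre-dose positive would also be visible, because 9.1.2 and 9.5 list the levels. That is true, but a listing does not say how the subject counts in the primary percentage.

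The SAP, which is not at hand, may add a sensitivity analysis. The absence of one from a protocol would not by itself be a fault. The endpoint and the evaluable population, however, are defined in the protocol, and neither refers to the pre-dose titer.

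The 10 mIU/mL threshold is defined on the total titer, and replacing it by observed minus baseline would change the question. A subject at 12 with a baseline of 3 would be failed despite a protective level. That stands, so a corrected proportion belongs beside the primary result and not in its place.

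From 5.3.1 ("However, subjects who fail the first screening evaluation are allowed to be re-screened once") a reader might infer that a seropositive subject can slip in on a second reading. The text does not support this: a re-screened subject must again meet every criterion, including a negative anti-HAV result, and a documented vaccinee fails exclusion 1 again. No change to re-screening is called for.

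**Conclusion.** The point holds as a modest, inexpensive improvement. Seronegativity rests on the screening serology alone, and the Day 1 pre-dose titer enters neither the primary proportion nor the evaluable population. A subject with measurable pre-dose antibody would have no deviation and could be counted as protected by the product.

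The size is about 5 points per subject at n = 20, or 3.6 at n = 28, when a success would otherwise be a failure, and always in the product's favour. If no subject has pre-dose antibody, the result is unchanged.

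A reader might take the rise from 30% to 89% in the working as the expected bias. It is not. It holds for one subject at minimum potency, with assumed V/F, CV and a constant baseline of 4 mIU/mL, none of which the protocol gives. At twice the minimum potency the same baseline moves the probability only from 97% to 100%. Nor do the documents show that any affected subject would be enrolled.

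**What to change.** - **9.7.2:** require the Day 1 pre-dose quantitative anti-HAV result (sample 01) to be below the assay's quantification limit for inclusion in the evaluable population. State that limit, which the protocol does not give.
- **9.1.2:** keep the total-titer proportion as primary. For the safety population, report beside it a sensitivity proportion, either on baseline-corrected titers (observed minus pre-dose) or excluding subjects with measurable pre-dose antibody. Say in advance which.

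The cost is wording only, since sample 01 is already drawn and measured. The downside is that a subject or two may leave the evaluable set, or the percentage may become slightly less favourable. If every pre-dose result is below the limit, the figures stay as they are and seronegativity at dosing is shown on the endpoint's own assay.

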4. Subject with prolonged International Normalized Ratio (INR) or activated partial thromboplastin time (aPTT) at the screening visit
5. Subject with a platelet count below $100 \times 10^9/L$ at the screening visit
6. Subject suffering from some acute or chronic medical, surgical or psychiatric significant condition or laboratory abnormality at the screening visit or prior to study treatment administration that, according to Investigator judgement, may increase the risk associated with study participation or study treatment administration, or may interfere with the successful completion or interpretation of the study results
7. Subject with a history of the following: angioedema, cardiac arrhythmia, angina pectoris, myocardial infarction, cerebrovascular accident, cardiac failure, thrombotic events, embolism, coagulopathy, diabetes mellitus, hyperlipidaemia, nephrotic syndrome, acute renal injury, chronic obstructive pulmonary disease, asthma, hepatic disease, reticuloendothelial system dysfunction, or nervous system disorder
8. Subject with known personal or family history of abnormal bleeding episodes
9. Subject not willing to receive study treatment via IM route of administration or unable to receive study treatment via IM route of administration
10. Subject with cardiovascular risk factors based on medical history: active tobacco smoking and/or ongoing diabetes mellitus at the screening visit
11. Subject with thrombosis risk factors: prolonged immobilization within 2 months prior to the screening visit, history of venous or arterial thrombosis, use of estrogens (30 days prior to the study drug administration), indwelling central vascular catheters and

- hyperviscosity or hypercoagulable states
12. Subject with known history of hypersensitivity/allergic reaction to blood/plasma products
 13. Subject with known selective Immunoglobulin A (IgA) deficiency (with or without antibodies to IgA)
 14. Subject who received any plasma-derived product infusion within 12 months prior to study treatment administration
 15. Subject who received a blood or plasma transfusion within 12 months prior to study treatment administration
 16. Subject with systolic blood pressure >140 mmHg or diastolic blood pressure >90 mmHg at the screening visit and prior to treatment administration
 17. Subject with anemia (hemoglobin <12 g/dL in women and 13 g/dL in men) at the screening visit

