2.6 Study Population

The study population will consist of HAV-seronegative healthy male and female subjects. Subjects must meet all the inclusion criteria and none of the exclusion criteria at the screening visit to be eligible for participation in this study. Continued eligibility will be assessed upon admission to the clinical site, prior to study treatment administration.

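### Exclusion 16 joins its two blood-pressure occasions with 'and', so read literally a high pre-dose reading cannot exclude a subject who was normal at screening

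*Protocol*

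**What the plan says.** Protocol 5.2, exclusion 16, reads: "Subject with systolic blood pressure >140 mmHg or diastolic blood pressure >90 mmHg at the screening visit and prior to treatment administration". The synopsis carries the same text. Under 5.2, meeting any single exclusion criterion makes a subject ineligible.

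Section 2.6 says how the criteria are to be applied. Subjects must meet "none of the exclusion criteria at the screening visit to be eligible for participation in this study", and then: "Continued eligibility will be assessed upon admission to the clinical site, prior to study treatment administration". Section 7.3.1 follows this through: blood pressure is taken at screening, on Day -1 (when the eligibility criteria are reviewed again) and on Day 1 before the injection.

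Two other exclusions name the same two occasions. Exclusion 6 refers to a condition or "laboratory abnormality at the screening visit or prior to study treatment administration", and exclusion 26 (urine drug panel) also joins the occasions with *or*.

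**The concern.** A criterion that requires a high reading on both occasions does not do what a two-stage eligibility check is for. The second check can only confirm an exclusion already signalled at screening; it cannot find a new one. Nor can the criterion be decided at screening, because half of it has not yet been observed. That does not fit 2.6, which expects the exclusions to be settled at screening and then checked again. It also does not fit 5.3.1, which makes a subject who fails the criteria at screening a screen failure.

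What is at stake is the safety of dosing. The subjects are healthy volunteers who, by section 2.3, gain nothing medically from the product. Section 12.2 allows no waivers of the eligibility criteria, so the exact words decide whether dosing a subject with a single high reading is permitted or is a deviation. Two careful members of site staff could decide the same case differently.

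**Working it through.** The protocol gives no figure to reproduce here; the check is one of logic and of comparing sections.

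**Truth table.** Let S mean above 140 systolic or 90 diastolic at screening, and P mean the same before treatment. The literal criterion is *S and P*; the apparent intent is *S or P*.

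| Screening | Pre-dose | Excluded under *and* (as written) | Excluded under *or* |
|---|---|---|---|
| normal | normal | no | no |
| normal | high | **no** | **yes** |
| high | normal | **no** | **yes** |
| high | high | yes | yes |

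- Normal at screening (2 patterns): *and* excludes 0, *or* excludes 1.
- High at screening (2 patterns): *and* excludes 1, *or* excludes 2.
- In total: *and* 0 + 1 = 1 of 4; *or* 1 + 2 = 3 of 4.

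The two readings differ in exactly the two discordant rows. As an invented illustration, a subject at 138/88 mmHg at screening and 165/100 mmHg before the injection falls in the second row and does not meet exclusion 16 as written.

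**Which reading was meant.**

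1. Three exclusions name these two occasions: 6, 16 and 26. Two use *or*; only 16 uses *and*.
2. Section 2.6 applies the exclusions at screening and has eligibility assessed again on admission. *S or P* works under that procedure. *S and P* does not, since it is undetermined until the second reading.
3. The list uses *and* loosely elsewhere. Exclusion 11 ends its list of separate thrombosis risk factors with "indwelling central vascular catheters and hyperviscosity or hypercoagulable states". Exclusion 19 names AST together with "alanine aminotransferase [ALT] and gamma-glutamyl transferase [GGT]) levels greater than the upper limit of normal at screening visit", where it is implausible that all three enzymes must be raised together.

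All three points indicate a wording slip for a limit that applies on each occasion.

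**What else would stop the subject.** There are 8 inclusion + 29 exclusion = 37 criteria. Exclusion 16 is the only one with a blood-pressure number; the other 37 - 1 = 36 have none. Inclusion 5 asks for "Subjects in good health in the judgment of the Investigator, as determined by medical history, physical examination, vital signs, ECG and laboratory assessments", and exclusion 6 covers significant conditions that the Investigator thinks raise the risk. Both can catch the subject in the second row, but only by judgement.

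**The case against.** The strongest reply is that the strict reading is the less natural one. The phrase can be taken as a list of the times at which the limit is checked, and sections 2.6, 5.3.1 and 7.3.1 steer a site towards that meaning. A site may well apply the criterion as intended. This stands as an account of the intent, and it is why the point is treated as a wording slip and not as a deliberate rule. It does not make the wording safe: the neighbouring criteria say *or* for the same two occasions, so a careful reader has reason to think the difference is meant.

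Second, judgement remains available through inclusion 5 and exclusion 6, and 5.3.2 lets the Investigator or sponsor remove a subject at any time. That is true, but none of these sets a number, and the protocol chose to set one.

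Third, section 2.3 does not name blood pressure among the product's risks, and no practical effect is shown. Both are fair. The pattern counts only restate the logic, and the protocol gives no basis for estimating how many of the approximately 28 subjects would have discordant readings.

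Fourth, changing one word does not say whether the Day -1 or the Day 1 reading governs, or whether a repeat is allowed. That is correct, but the present wording is equally silent, so the change makes nothing worse.

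**Conclusion.** The concern holds. As written, exclusion 16 excludes 1 of the 4 high/normal patterns instead of 3, and among subjects normal at screening it excludes none. The size is limited: investigator judgement remains as a backstop, and the anti-HAV endpoint, the PK analysis and the sample size rationale are untouched. What is lost is the only fixed blood-pressure limit at the point of dosing. The conclusion about the wording rests on reading the text literally; the conclusion about intent rests on 2.6 and on exclusions 6 and 26. No assumption is made about how often readings would disagree. It should be corrected because it is an operative eligibility rule and the correction costs almost nothing.

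**What to change.** In exclusion 16, in 5.2 and in the synopsis, replace the *and* between the two occasions with *or*, so that a reading above the limit at either time excludes the subject. This matches exclusions 6 and 26. The thresholds, the measurement times and all other criteria stay as they are, and the readings needed are already scheduled.

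The cost is one word in two places. The downside is that an occasional subject will be deferred or excluded because of a transient high reading; a subject who fails at screening may be re-screened once under 5.3.1.
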